The aim of this six-week double-blind, placebo-controlled clinical trial was to provide evidence of the clinical efficacy of SmartMouth Clinical DDS Advanced Oral Rinse (SM) in comparison with the efficacy of 0.12% chlorhexidine rinse (CHX) and a placebo rinse (PL). The outcomes included measures of plaque, gingivitis, tooth staining, calculus formation, patient compliance, and taste perception.

Materials and Methods:

A six-week, double-blinded, clinical study will be conducted on 80 subjects diagnosed with plaque induced gingivitis and/or chronic periodontitis. The study will take place at two centers: Saint Louis University Center for Advanced Dental Education (Site 1) and Southern Illinois University School of Dental Medicine (Site 2). The study was approved by the Institutional Review Boards (IRB #25867) at Saint Louis University and Southern Illinois University Edwardsville.

Subjects who sign the informed consent and medical history forms and meet the preliminary entrance criteria will be examined at baseline (visit 1). All participants will be informed of the nature of the study, its purpose, and any possible risks. Subjects will be informed as to the length of the study and the specific procedures that would be performed. Subjects will be informed that this was a voluntary study and that they are free to withdraw from the study at any time.

Gingival index (GI) will be measured using the Loe and Silness method.²⁴ The gingiva will be scored at six sites of each tooth (distobuccal, buccal, mesiobuccal, distolingual, lingual, mesiolingual) and given a score from 0 – 3. By adding the scores and dividing by the total number of sites, the GI for the patient will be obtained.

Sites with GI scores of 2 or 3 will be counted as bleeding. A whole mouth total Bleeding Score (BS) will be calculated by summing the number of bleeding sites and dividing by the number of teeth.

Extrinsic tooth stain will be scored on the facial surfaces of the eight incisor teeth using a modification of the Lobene tooth stain index (TSI).²³ Each incisor will be scored for stain area on a scale of 0-3. The sum of the stain scores for the subject will be used as that subject's stain score.

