Supragingival calculus on the lingual surfaces of the six mandibular anterior teeth will be scored using the Volpe-Manhold calculus index (CI).³⁶ Supragingival calculus height in three defined planes on the lingual surface of each tooth will be measured using a periodontal probe. The measurements will be added and a mean subject score calculated.

Plaque will be scored based on the Turesky modification of the Quigley—Hein Plaque Index (PI).³³ A score of 0 – 5 will be assigned to six sites of each tooth (distobuccal, buccal, mesiobuccal, distolingual, lingual, mesiolingual) following the use of a disclosing solution. The Plaque Index for the entire mouth will be determined by dividing the total score by the number of surfaces examined.

Teeth with gross caries and third molars will not be scored. A complete periodontal examination will be performed for all subjects that meet the inclusion criteria. A panoramic radiograph will be taken for all subjects who do not have full mouth radiographs within the last year. Safety assessments will be made at each measurement visit.

Visit 2 will occur within four weeks of Visit 1. For this relatively small clinical study for which there are two centers and three treatments, subjects will be assigned treatments through the process of minimization to assure a balance in the number of subjects in each treatment group: Group 1 SM, Group 2 CHX or Group 3 PL. PL will be identical to SM, except it will not contain cetylpyridinium chloride, zinc chloride and sodium chlorite. Each group will consist of approximately 25 subjects. All subjects will be given a complete dental prophylaxis to remove plaque, calculus, and stain. Written and verbal oral hygiene instructions will be given that will includ a regular regimen of brushing twice daily and flossing daily. All subjects will be assigned a commercially available ADA accepted toothbrush and dental floss. They will be given a three-

week supply of the assigned mouth rinse with written and verbal instructions for use. Subjects will be instructed not to have their teeth professionally cleaned prior to study completion.

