All mouth rinses will be in a plain package and dispensed by the faculty investigators. The package will be labeled with a code to indicate the product. Only the faculty investigators will have access to the code information. Group assignment will be performed by one of the investigators who will use the process of minimization and will not be aware of the periodontal health of subjects. Directions for use are contained in the package. The examiners will not see the product. The examiners will give instructions for mouth rinse use, but they will not be aware which rinse the subjects are using. Each product will contain two solutions which are mixed prior to use.

Subjects will be examined again at visit 3, three weeks after visit 2. All clinical measurements will be repeated. Each subject will return the unused rinse. Additional rinse will be given to each subject after visit 3 for use until the final visit. Compliance will be determined by regulating the amount of rinse dispensed on a 3 week basis and by the measurement of any unused rinse (compliance defined as percentage of product used).

Subjects will be examined again at visit 4, three weeks after visit 3. Clinical measurements will be repeated. Each subject will return the unused rinse. Compliance will be determined by the measurement of any unused rinse at the end of the study. Subjects will be given a Taste Perception Survey to answer questions about their experience with the mouth rinse.

Following the study, the subjects will be treated by their provider's discretion. Subjects can withdraw from the clinic trial at any time without providing reason. The investigators can also withdraw subjects at any time due to protocol irregularity. All instances of withdraw will be documented.

Intra-Examiner Calibration

Intra-examiner calibration will be completed prior to beginning the study. Three examiners ([name]) will make original and repeat determinations of values for four teeth in ten subjects for each of four indices. A kappa value will be determined for each original and repeat determination, and the average kappa value will be determined for the four teeth for each index for each examiner. For an examiner to be considered calibrated, average kappa values for each index have to be between 0.81 and 1 (almost perfect agreement).

Data Analysis

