The primary outcome measures are gingivitis and plaque. Secondary outcome measures are tooth discoloration, taste perception, malodor and calculus. For each outcome measure, a single value will be calculated for each subject—that is, the subject is the unit of measurement for analyses.

Analyses will be based on intention to treat (with randomized intervention). Sensitivity analyses will be based on as treated analyses. To test for differences among and between treatments, we will

use repeated measures analysis of variance (ANOVA) with treatment and location as the between-group factors and one within-subject (repeated-measures) factor with 2 levels: (1) measurements at visit 3 and (2) measurements at visit 4. For these analyses, we will use multivariate analysis of variance (MANOVA), which does not require the assumptions of compound symmetry (homogeneous pooled within-group variances and across-subjects covariances) and sphericity (orthogonal components). Post-hoc testing will be performed with the Tukey honestly significant difference ([HSD] test.

Sample-size calculation and power analysis (treatment effect of Smart Mouth ACF): One goal of the proposed study is to test the null hypothesis that the mean gingival score for Smart Mouth ACF is equal to the mean gingival score for the placebo (control). With alpha (the criterion for significance) set at 0.05, a 2-tailed test (which means that an effect in either direction will be interpreted), and a sample size of 20 and 20 for the two groups, the study will have a power of 99.9% to yield a statistically significant result. This computation is based on data from Ayad et al (2011), with the assumption that the mean difference is 0.44 (corresponding to means of 2.03 versus 1.59) and a common within-group standard deviation of 0.27 (based on SD estimates of 0.22 and 0.31). We assume that this effect size is reasonable, in the sense that an effect of this magnitude is anticipated in this field of research. We could report an observed difference of 0.44 with a 95.0% confidence interval of 0.27 to 0.61. Based on plaque scores given in Ayad et al (2011) and a sample size of 20 in each group, we would have a power >99.9% to demonstrate a treatment effect for Smart Mouth ACF. Our intent is to enroll 25 subjects into each group. Our sample-size calculations assume a 20% dropout rate. We, however, anticipate that the dropout rate will be less than 10%.

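### The gingival index model omits the visit 1 score; the analysis stays valid but may give up precision in the SM versus CHX equivalence comparison

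*Combined protocol and SAP*

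**What the plan says.** Under Materials and Methods, consenting subjects who meet the preliminary criteria "will be examined at baseline (visit 1"), and GI is defined there as one averaged score per subject. Allocation is described with visit 2, up to four weeks later, by a "process of minimization to assure a balance in the number of subjects in each treatment group". The investigator who allocates does not know the subjects' periodontal health. Also at visit 2, "All subjects will be given a complete dental prophylaxis to remove plaque, calculus, and stain", and hygiene instruction is given. At visit 3, "All clinical measurements will be repeated", and they are taken once more at visit 4.

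Under Data Analysis, the one comparative model is a repeated-measures ANOVA, fitted by MANOVA. Treatment and location are the between-subject factors, and there is "one within-subject (repeated-measures) factor with 2 levels: (1) measurements at visit 3 and (2) measurements at visit 4". It is introduced with the words "To test for differences among and between treatments". The only sensitivity analysis is as treated and adds no covariate.

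The closing paragraph of that section plans SM versus CHX equivalence on gingivitis: margin 0.20, SD 0.25, 21 per group, one-tailed alpha 0.05, power 81.7%. It then restates the rule as a 95% confidence interval. It does not say which model supplies that interval.

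**The concern.** A pre-allocation measurement of a primary outcome will already be in hand, and the model ignores it. The design does not compensate: the stated aim of the minimization is balance in group numbers, so visit 1 GI is balanced only by chance. This causes no bias, because the allocator cannot act on periodontal health. If visit 1 GI predicts later GI, however, the residual variance is larger than it need be.

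The equivalence comparison is where that would be felt. Its stated 81.7% is the power of a single one-sided test. On the same inputs, two one-sided tests at 0.05 have 63.4% power, and the 95% interval rule has 43.1%. Precision is scarce there, so data already collected are worth using if r is at least moderate.

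**Working it through.** **Inputs from the Data Analysis section.** Equivalence: n = 21 per group, SD 0.25, margin 0.20, true difference 0, one-tailed alpha 0.05. SM versus placebo: n = 20 per group, difference 0.44, SD 0.27, two-sided 0.05. Enrolment is 25 per group, with dropout expected below 10%.

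**Assumptions not in the documents.** r runs from 0 to 0.7. When the two visits are averaged, the between-visit correlation ρ runs from 0.5 to 0.8, and 0.25 is taken as the single-visit SD.

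**Step 1: reproduce the plan's figure.** SE = 0.25 × √(2/21) = 0.0772, with 40 df. A single one-sided t test against 0.20 (noncentral t) has power 81.7%, as stated. Two one-sided tests at 0.05 give 63.4%. Requiring the whole 95% interval to lie inside ±0.20 gives 43.1%.

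**Step 2: adjust for visit 1 GI.** N is the number analysed and G the number of group cells:

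SE = SD × √(1 − r²) × √[(2/n)(1 + 1/(N − G − 2))], with N − G − 1 df.

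The last factor is the cost of estimating the slope. With N = 42 and G = 2 it is 1 + 1/38, with 39 df. Single follow-up score, n = 21:

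| | One-sided 0.05 | Two one-sided tests, 0.05 | 95% interval rule |
|---|---|---|---|
| Unadjusted | 81.7% | 63.4% | 43.1% |
| r = 0 | 80.8% | 61.5% | 40.8% |
| r = 0.1 | 81.1% | 62.2% | 41.7% |
| r = 0.2 | 82.1% | 64.3% | 44.3% |
| r = 0.3 | 83.9% | 67.8% | 48.8% |
| r = 0.5 | 89.6% | 79.2% | 64.3% |
| r = 0.7 | 97.0% | 93.9% | 87.5% |

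Simulated ANCOVA (40,000 runs) agrees: for two one-sided tests at 0.05 it gives 61.6% at r = 0, 67.6% at r = 0.3 and 79.2% at r = 0.5.

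**Step 3: match the planned two-visit, three-arm model.** The SD of the two-visit average is 0.25 × √((1 + ρ)/2), which is 0.2165 at ρ = 0.5 and 0.2372 at ρ = 0.8. Under 10% dropout from 25 leaves about 23 per group. With three arms and two sites, N = 69 and G = 6, giving 62 df and a slope factor of 1 + 1/61. Each range below runs from ρ = 0.8 to ρ = 0.5.

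| | n = 21, two arms, two one-sided tests 0.05 | n = 23, three arms, two one-sided tests 0.05 | n = 23, three arms, 95% interval rule |
|---|---|---|---|
| Unadjusted | 70–81% | 76–85% | 61–74% |
| r = 0 | 69–79% | 75–85% | 60–73% |
| r = 0.3 | 74–84% | 80–89% | 67–79% |
| r = 0.5 | 84–91% | 89–94% | 79–88% |

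**Step 4: break-even.** On the SE, r = √(1 − 1/(slope factor)), which is 0.160 for N = 42, G = 2 and 0.127 for N = 69, G = 6.

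**Step 5: SM versus placebo.** Power is 99.89% unadjusted, 99.86% adjusted at r = 0 and 99.94% at r = 0.3, so nothing practical is gained.

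**The case against.** The plan contains no error of validity here; leaving out a baseline covariate is a legitimate prespecified choice. The gain rests on an r that the documents do not give, and they supply reasons for it to be low: visit 1 may precede visit 2 by four weeks, and everyone then has a prophylaxis and hygiene instruction. No GI is scheduled between the prophylaxis and the start of rinsing.

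The 63.4% and 43.1% describe two arms and one visit. On the model actually planned, unadjusted power is already 76–85% for two one-sided tests. Most of the fall from 81.7% comes from a different fault: one-sided power is presented as equivalence power, and a one-tailed 0.05 is paired with a 95% interval. Finally, the model is offered for testing differences, so its link to the equivalence interval is an inference.

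All of this stands, and it limits the priority of the point. It does not remove it. Because r is unknown beforehand, the choice has to be made on the balance of outcomes: at r = 0 the loss is 1.9 points for two one-sided tests (63.4% to 61.5%) and 2.3 under the 95% interval rule (43.1% to 40.8%) in the least favourable case worked. The gain is several times that if r reaches 0.5. Adding the covariate after seeing the data would look selective. That no model is named for the equivalence interval is a further reason to write the sentence.

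**Conclusion.** The point holds as a possible loss of precision, not as bias. It is a change that should be made, held with medium confidence because r is unknown. For SM versus CHX equivalence with the two visits averaged, adjustment adds about 3 to 4 points of power at r = 0.3 and 9 to 14 at r = 0.5 (two one-sided tests at 0.05). It costs about 1 to 2 points at r = 0. These figures assume a true difference of zero, a single-visit SD of 0.25 and ρ between 0.5 and 0.8.

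No benefit is shown for plaque. The prophylaxis removes it, no plaque equivalence margin is stated, and plaque power for the SM treatment effect is already above 99.9%. Adjustment also does not settle the conflict between the two error levels in the equivalence paragraph.

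**What to change.** In Data Analysis, for GI:

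- Add the subject's visit 1 GI as a prespecified covariate in the repeated-measures model, beside treatment, location and visit (3 or 4).
- State that the Tukey (Tukey-Kramer) comparisons use the baseline-adjusted treatment means.
- State that the SM versus CHX equivalence interval comes from those same means, and whether it refers to visit 4 or to the average of visits 3 and 4.
- Report the present unadjusted model as a sensitivity analysis.

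The same covariate may be used for the plaque index for consistency, but this is optional. The level of the equivalence interval (one-sided 0.05 or 95%) needs its own, separate correction.

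The cost is SAP wording and one degree of freedom, with no new data, plus the small loss of equivalence power shown above if r proves near zero.

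### MANOVA on visits 3 and 4 has no missing-visit rule and, as usually run, discards subjects seen only at visit 3; a mixed model would keep them for a modest gain at almost no cost

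*Combined protocol and SAP*

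**What the plan says.** The Data Analysis section names gingivitis and plaque as primary outcomes. Treatments are compared by repeated measures ANOVA, with treatment and location as between-group factors and a within-subject factor "with 2 levels: (1) measurements at visit 3 and (2) measurements at visit 4". The method is then specified: "we will use multivariate analysis of variance (MANOVA), which does not require the assumptions of compound symmetry". Pairwise comparisons use Tukey's HSD.

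The analysis population is set by "Analyses will be based on intention to treat (with randomized intervention" and the only sensitivity analysis is as treated. Neither statement says what happens when one of the two visits is missing, and nothing else in the document does.

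Materials and Methods provides for a full examination at visit 3 ("All clinical measurements will be repeated"), three weeks before visit 4. It also states "Subjects can withdraw from the clinic trial at any time without providing reason" and "The investigators can also withdraw subjects at any time due to protocol irregularity". The sample-size paragraph adds "Our sample-size calculations assume a 20% dropout rate", followed by "We, however, anticipate that the dropout rate will be less than 10" percent.

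**The concern.** A subject who attends visit 3 and then leaves has valid values on both primary outcomes. Standard MANOVA works on complete response vectors and deletes that subject. This fits poorly with an intention-to-treat analysis, and without a written rule the handling could be settled after the data have been seen.

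The main stake is precision on the two primary outcomes. A second, conditional stake is bias: if loss depends on the visit 3 score and differs between arms, the complete pairs are a selected group. The documents give no evidence that this will happen.

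The plan prefers MANOVA because it avoids compound symmetry and sphericity. With two levels there is only one within-subject difference, so sphericity cannot fail. A mixed model with an unstructured 2×2 covariance assumes neither condition, so the plan's own reason does not favour MANOVA.

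**Working it through.** **Inputs from the Data Analysis section.** 25 enrolled per arm; 20 per arm after 20% dropout; gingival difference 0.44; SD 0.27; two-sided alpha 0.05.

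**Assumptions, because the documents are silent.** Between-visit correlation r = 0.5 (range 0.3 to 0.8), the split of losses before and after visit 3, and loss unrelated to outcome unless stated.

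**The plan's own figures reproduce.** The SE at 20 per group is 0.27 × √(2/20) = 0.0854. The noncentrality is 0.44/0.0854 = 5.15 on 38 df, giving power 99.89% (plan: 99.9%). The 95% interval is 0.267 to 0.613 (plan: 0.27 to 0.61). The dropout allowance also fits: 25 × 0.8 = 20.

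**Formulas.** The contrast is the treatment difference averaged over visits 3 and 4, which is the treatment main effect of the planned ANOVA. Let n3 be the number per arm seen at visit 3 and nc the number seen at both visits.

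- Complete pairs, variance per arm: SD²(1+r)/(2nc)
- Mixed model, variance per arm: (SD²/4) × [(1+r)²/n3 + (1−r²)/nc]
- SE of the difference: √(2 × variance per arm)

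For five lost per arm after visit 3 at r = 0.5:

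- Complete pairs: 0.0729 × 1.5/40 = 0.002734, SE 0.0739.
- Mixed model: 0.018225 × (2.25/25 + 0.75/20) = 0.002324, SE 0.0682.

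| Lost per arm | n3 | nc | SE, complete pairs | SE, mixed model | Reduction |
|---|---|---|---|---|---|
| 5, all after visit 3 | 25 | 20 | 0.0739 | 0.0682 | 7.8% |
| 5, of whom 2 after | 22 | 20 | 0.0739 | 0.0714 | 3.5% |
| 5, all before visit 3 | 20 | 20 | 0.0739 | 0.0739 | 0 |
| 2, all after visit 3 | 25 | 23 | 0.0690 | 0.0669 | 3.0% |
| 2, of whom 1 after | 24 | 23 | 0.0690 | 0.0679 | 1.6% |

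Over r = 0.3 to 0.8, the first row ranges from about 7% to 9% and the fourth from about 3% to 4%.

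**Check by fitting the model.** REML was fitted to simulated trials with three arms, location, visit, treatment-by-visit and unstructured covariance. With five lost per arm after visit 3 (1,500 replicates), the mean model SE was 0.0739 for complete pairs and 0.0679 for REML. With two lost (1,000 replicates), it was 0.0687 and 0.0666.

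**Visit 4 alone.** The mixed-model variance per arm is SD²[(1−r²)/nc + r²/n3], against SD²/nc for complete pairs. At r = 0.5 the SE falls by 2.5% with five lost per arm and by 1.0% with two, all after visit 3.

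**Bias, as illustration only.** Take SD 0.25, r = 0.6, true difference 0, and 2 of 25 lost from one arm only, with loss weight multiplied by e per SD of visit 3 score. The complete-pair contrast is off by about 0.016 (0.013 to 0.017 for r 0.3 to 0.8) and the likelihood estimate by about 0.001 or less. If both arms lose subjects in the same way, the complete-pair bias is about 0. If loss instead follows the unseen visit 4 score, missing at random fails: complete pairs are off by 0.015 and the likelihood estimate by 0.007.

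**The case against.** The strongest reply is that no conclusion is shown to change. Superiority over placebo is overwhelmingly powered even at 20 per group, and the enrolment of 25 already pays for losing five. At the anticipated dropout of under 10%, about two per arm, the SE moves by only 0.001 to 0.002 on a 0–3 index. The 8% figure needs about twice that dropout, all of it after visit 3. All of this stands, and is why the gain is called modest.

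A trial described as lasting six weeks might care more about visit 4, where the gain is smaller. The precision figures also assume random loss. In simulations with balanced loss tied to the visit 3 score (r 0.5 and 0.7), the averaged-contrast SD ratio, mixed model to complete pairs, was only 0.96 to 0.99, and the visit 4 ratio was 1.00 to 1.05. These limits stand too. The averaged contrast is nevertheless the one the planned ANOVA tests as its treatment effect.

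The plan does not state listwise deletion, and one sentence could supply a missing-visit rule without changing the model. That is fair, but a rule that keeps MANOVA must either delete the incomplete subjects or impute for them. The mixed model uses their data directly. The bias argument is hypothetical and carries little weight in the conclusion.

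**Conclusion.** The concern holds. The plan has no missing-visit rule, its own withdrawal and dropout provisions make visit-3-only subjects foreseeable, and its chosen method as usually run removes them from both primary analyses. The cost is a modest loss of precision: about 3% in the SE of the visit-averaged difference at two losses per arm and about 8% at five, if all come after visit 3. It is less if some leave earlier and nothing if all do. These figures rest on r = 0.5 and random loss, neither of which the documents give.

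Superiority over placebo is not threatened, and no claim is made here about power for equivalence with chlorhexidine. The change should be made because it is nearly free, not because the main result is in danger.

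**What to change.** Replace MANOVA with a linear mixed model fitted by REML:

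- Fixed effects for treatment, location, visit and treatment-by-visit. The plan does not settle whether treatment-by-location terms were intended; they can be added if so.
- Unstructured 2×2 within-subject covariance.
- Small-sample degrees of freedom, for example Kenward-Roger.
- Tukey-adjusted pairwise treatment contrasts.
- Every randomized subject with at least one of visits 3 and 4, analysed in the assigned group.

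State the missing-at-random assumption. Report by arm how many were lost before visit 3, since this model does not recover them.

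The cost is a few sentences and a different standard procedure, with no new data, subjects or visits. With no missing visits and arms balanced by location (13/12), the visit-averaged contrast matched the complete-data contrast to within 1e-15. The downside is slightly more analysis work and reliance on missing at random, which is weaker than what the complete-pair analysis needs.

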Equivalence of Smart Mouth ACF with 0.12% chlorhexidine. We will have power of 82% to demonstrate that the mean gingivitis score for Smart Mouth ACF is the same (neither lower nor higher) than the mean for .12% chlorhexidine. This assumes that the mean values for the two treatments are equal, with a common within-group standard deviation of 0.25, that a difference of .20 points or less is unimportant, that the sample size in the two groups will be 21 and 21, and that alpha (1 tailed) is set at .05. For this calculation, we used standard deviations from Ayad et al (2011). Formally, the null hypothesis is that the mean for Smart Mouth ACF is 0.20 points lower or higher than the mean for .12% chlorhexidine, and the study has power of 81.7% to reject this null. Equivalently, the likelihood is 81.7% that the 95.0% confidence interval for the mean difference will exclude a difference of 0.20 points in either direction.

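### Enrolment is given as both 80 and three groups of 25 (75), and 25 per group at the assumed 20% dropout leaves 20 completers, not the 21 used for equivalence

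*Combined protocol and SAP*

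**What the plan says.** All the statements are in the combined protocol and SAP.

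- **Materials and Methods, opening paragraph:** the "clinical study will be conducted on 80 subjects".
- **Materials and Methods, visit 2:** assignment by minimization is meant "to assure a balance in the number of subjects in each treatment group: Group 1 SM, Group 2 CHX or Group 3 PL", and "Each group will consist of approximately 25 subjects".
- **Data Analysis, sample-size paragraph:** SM against placebo is powered at 20 and 20. The paragraph then says "Our intent is to enroll 25 subjects into each group" and "Our sample-size calculations assume a 20% dropout rate". The next sentence adds a more hopeful expectation: "We, however, anticipate that the dropout rate will be less than 10" percent.
- **Data Analysis, equivalence paragraph:** the comparison with 0.12% chlorhexidine assumes "that the sample size in the two groups will be 21 and 21", SD 0.25, a margin of 0.20, no true difference and a one-tailed alpha of 0.05. The stated power is 81.7%, rounded to 82%. No derivation of 21 is given.

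**The concern.** Three balanced groups of 25 make 75 subjects, so the plan carries two enrolment totals. It also carries two completer counts for the same SM arm: 20 in the placebo comparison and 21 in the chlorhexidine comparison. The sentence on 20% dropout speaks of the calculations in general, yet only the count of 20 follows from 25 enrolled at that rate.

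Two things are at stake. A reader cannot tell whether full recruitment means 75 or 80. And the equivalence comparison, which has little power to spare, rests on a sample that the stated group size and dropout rate do not deliver. The placebo comparison has ample power at 20 per group and is unaffected.

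**Working it through.** **Inputs.** From Materials and Methods: 80 in total, three balanced groups, about 25 each. From the sample-size paragraph: 25 per group, 20% dropout assumed, below 10% expected; n = 20 and 20, difference 0.44, SD 0.27, two-sided alpha 0.05. From the equivalence paragraph: n = 21 and 21, SD 0.25, margin 0.20, true difference 0, one-sided alpha 0.05.

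**1. Reproduce the plan's power figures.**

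*SM against placebo, n = 20.* Standard error = 0.27 × √(2/20) = 0.0854. Noncentrality = 0.44 / 0.0854 = 5.15. The two-sided t-test on 38 df has power 99.89%, against the stated 99.9%. The 95% interval is 0.44 ± 2.024 × 0.0854, or 0.27 to 0.61, as stated.

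*Equivalence, n = 21.* Standard error = 0.25 × √(2/21) = 0.0772. Noncentrality = 0.20 / 0.0772 = 2.592. The critical value on 40 df is 1.684. Power = P(noncentral t > 1.684) = 81.68%, which is the stated 81.7%. The plan's figure is therefore the power of one one-sided t-test.

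**2. Compare the counts.**

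- 3 × 25 = 75, against 80: a difference of 5.
- 25 × (1 − 0.20) = 20, which equals the n in the placebo comparison.
- 21 / 25 = 0.84, so 21 completers out of 25 would mean 16% dropout, a rate that appears nowhere.
- 21 / 0.80 = 26.25, so 27 enrolled per group would be needed for 21 completers at 20% dropout. That is 81 in total.
- 80 / 3 × 0.80 = 21.3.

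**3. Equivalence power at the counts in play, by the plan's method** (one one-sided t-test, df = 2n − 2, noncentrality = 0.20 / (0.25 × √(2/n))).

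| Completers per group | How reached | Power |
|---|---|---|
| 20 | 25 enrolled, 20% dropout | 79.9% |
| 21 | as stated in the plan | 81.7% |
| 22 | 25 enrolled, dropout below 10%, rounded down | 83.3% |

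The last row is cautious: 25 × 0.90 = 22.5, so dropout below 10% leaves more than 22.5 on average. The step from 21 to 20 costs 81.68 − 79.94 = 1.7 points. It also shows that 21 is the smallest n that reaches 80% by this method.

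**4. Power for the hypothesis as the plan states it.** The equivalence paragraph sets a null that the means differ by 0.20 in either direction, so both one-sided tests must reject. With D the observed difference, S the pooled SD and t the critical value, power = P(|D| < 0.20 − t × S × √(2/n)), integrated over the distribution of S.

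| Completers per group | Two one-sided 0.05 tests | 95% interval excludes 0.20 both ways (one-sided 0.025) |
|---|---|---|
| 20 | 59.9% | 38.8% |
| 21 | 63.4% | 43.1% |

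The second column of results is included because the same paragraph also describes its power in terms of a 95% interval.

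**The case against.** Four points can fairly be made for the plan.

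*The group size is approximate.* The visit 2 text does say so, and 80 / 3 = 26.7 could pass as about 25. This softens that sentence, but the sample-size paragraph gives 25 without qualification, and its 20 completers are exactly 80% of 25. It states an intent, however, and neither place sets a point at which recruitment stops.

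*About 80 might be examined at visit 1 and about 75 assigned at visit 2, up to four weeks later.* This is possible, but the documents do not say it. The figure of 80 is given as the number on whom the study is conducted.

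*Dropout is expected to be below 10%.* This stands. At that rate 25 per group leaves more than 21, and the shortfall is gone. But the plan sets this expectation apart from the 20% that it says its calculations assume, and the conflict between 75 and 80 remains at any dropout rate.

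*The loss is one completer per group.* This also stands.

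A reader might go further and infer that the placebo power was worked out for a 75-subject trial and the equivalence power for an 80-subject trial. The 21.3 from step 2 fits that, but nothing in the documents ties 21 to 80. The other account, that 21 was chosen as the smallest n above 80% power, fits equally well.

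**Conclusion.** The inconsistency is real and minor. The enrolment figures differ by 5 subjects, and the equivalence sample exceeds by one per group what 25 enrolled and 20% dropout provide. Under those two inputs the plan's own method gives a power 1.7 points lower than stated, just under 80%. This rests on the plan's SD, margin and assumption of no true difference, and on equal allocation and dropout across the groups.

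The documents do not support the stronger conclusions that each power statement was built on a different enrolment total, or that the trial will necessarily fall short of 21 per group. No conclusion about SM against placebo changes.

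The gap between 81.7% and the two-sided figures in step 4 is a separate and larger matter, present at 20 and at 21 alike. It bears on this point only because replacing 21 by 20 and recalculating by the same one-sided method would leave a figure that does not answer the stated hypothesis.

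**What to change.** Give one enrolment total and one group size in Materials and Methods (opening paragraph and visit 2) and in the sample-size paragraph, and use the same completer number in both power calculations.

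If 25 per group is kept, change 80 to 75 and restate the equivalence calculation at 20 and 20. State which criterion will decide equivalence and give the power for it: about 60% with two one-sided 0.05 tests, or about 39% if the 95% interval must exclude 0.20 in both directions. The expectation of dropout below 10% can stay as a remark, marked as not being the planning assumption.

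If the sponsor would rather keep 21 completers in every group at 20% dropout, that needs 27 per group, 81 in total. A split of 80 into 27, 27 and 26 leaves 26 × 0.80 = 20.8 in one arm. The two-sided power would then be about 63% or 43%, and would still need to replace the 81.7%.

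Keeping 25 per group costs only wording, one recalculation and a less favourable stated power.
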